#### **Trial Schema ARMS ARM B: Four Expansion Cohorts** ARM A: Single Agent Safety Lead-In & Cycle 1 **B1.** Measurable NBL **DOSE LEVEL 1 B2. Evaluable NBL 0-1 DLTs** 30 mg/kg magrolimab RP2D magrolimab **B3.** Measurable + 17.5mg/m^2 $+ 17.5 \text{mg/m}^2$ Osteosarcoma dinutuximab with **B4.** Osteosarcoma dinutuximab safety lead-in w/resectable (6 patients) pulmonary only relapse DOSE LEVEL -1 0-1 ≥ 2 **DLTs DLTs STOP TRIAL** ≥ 2 DLTs

[figure not shown]

Figure 2: Trial Schedule Schema

If ≥2 DLTs at Dose Level 1 (after week 3 or week 6), then reduce to DL-1 (20 mg/kg) and assess for safety, If ≥ 2 DLTs at DL-1, then STOP study

A. After cycle 2, Hu5F9-G4 (magrolimab) will be administered on Day 1 of the 1st and 3rd week of every subsequent cycle. Cycles may be repeated in the absence of disease progression or toxicity to a maximum of 12 cycles.

A. After cycle 2, Hu5F9-G4 (magrolimab) will be administered on Day 1 of the 1st and 3rd week of every subsequent cycle. Cycles may be repeated in the absence of disease progression or toxicity to a maximum of 12 cycles.

B1: Measurable NB B2: evaluable NB

B3: measurable OS

B4: OS with resectable pulmonary only relapse

pulmonary metastasectomy after at least 1 cycle and will require delay in starting subsequent cycle (for a maximum of 5 cycles post resection)

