### 6.1.1.1 Safety Assessment During "single agent Safety Lead-In"

Patients aged ≥2 or < 18 years of age will be enrolled on the "single agent Safety Lead-In", and will receive a therapeutic dose of Hu5F9-G4 (magrolimab) (30 mg/kg IV) on Day 1 of weeks 2 and 3 for a 21-day "single agent Safety Lead-In" cycle (see **Figure 1** and **Figure 2**). An assessment for DLTs as defined in **Section 6.3** will be performed during and at the end of the 21-day "single agent Safety Lead-In".

Any patient who does not develop DLT during the "single agent Safety Lead-In" may proceed to Cycle 1 (combination therapy with Hu5F9-G4 (magrolimab) plus dinutuximab) and will be evaluable for safety assessment during and after Cycle 1. When dinutuximab is administered immediately after Hu5F9-G4 (magrolimab), redosing with acetaminophen and diphenhydramine is not necessary. The intravenous line should be flushed well between drug administrations.

Patient enrollment and start of treatment during the safety "single agent Safety Lead-In" assessment will be staggered by 7 days for each patient enrolled. Three patients will initially be enrolled at Dose Level 1 (30 mg/kg IV).

- If 0 of the initial 3 patients develops a DLT during the 21-day "single agent Safety Lead-In", the next phase of safety will be evaluated in Cycle 1 as outlined below (Section 6.1.1.2).
- If 1 of the initial 3 patients develops a DLT (Section 6.3) during the 21-day "single agent Safety Lead-In", then an additional 3 patients will be enrolled at Dose Level 1.
  - o If 0 of these 3 additional patients (totaling 1/6) develops a DLT during the 21-day "single agent Safety Lead-In", the study will continue to evaluate DLTs in Cycle 1 as outlined below (Section 6.1.1.2).
  - o If ≥1 of these 3 additional patients (totaling 2/6) develop a DLT, the dose of Hu5F9-G4 (magrolimab) will be de-escalated to Dose Level -1 (20 mg/kg) during weeks 2 and 3 in the next 3 patients. The safety of Dose Level -1 will be similarly evaluated in 3-6 patients.
- If ≥ 2 of the initial 3 patients develop a DLT during the 21-day "single agent Safety Lead-In", the dose of Hu5F9-G4 (magrolimab) will be de-escalated to Dose Level -1 (20 mg/kg) during weeks 2 and 3, in the next 3 patients. The safety of Dose Level -1 will be similarly evaluated in 3-6 patients.
- If ≥ 2 patients develop DLT during the "single agent Safety Lead-In" using Dose Level -1, enrollment will pause pending discussions with the sponsor, IRB and FDA.

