Any patient who develops a DLT during the "single agent Safety Lead-In" will be removed from additional therapy on this study.

#### 6.1.1.2 Safety Assessment During Cycle 1

An assessment for DLTs will be performed during and at the end of the 21 days of Cycle 1 (Figure 2). In the absence of

DLTs or progressive disease (PD), patients may proceed to a maximum of 12 cycles of combination therapy. After Cycle 2, each subsequent cycle will consist of Hu5F9-G4 (magrolimab) administered on Day 1 of weeks 1 and 3 of the cycle (week 2 will be a week of rest), with dinutuximab administration on Day 2 through 5 of week 1.

The initial dosing of each patient during Cycle 1 safety assessment will be staggered by 7 days for each patient. Three weeks (21 days) must elapse after completion of Cycle 1 in the final patient in the dose finding cohort (Arm A) to allow for safety assessment before treating additional patients at the determined recommended phase 2 dose (RP2D) in Arm B.

The following rules apply to the DLT assessment conducted at the conclusion of Cycle 1 (week 6).

If Dose Level 1 is selected as safe for Cycle 1 based on safety results from the 'Single agent Safety Lead-In', three patients will be enrolled, and the following applies:

- If 0 of the initial 3 patients develops a DLT during Cycle 1, the study will proceed to the expansion cohorts (Arm B) (see Section 6.4).
- If 1 of the initial 3 patients develops a DLT during Cycle 1, then an additional 3 patients will be enrolled at Dose Level 1
  - o If 0 of these 3 additional patients (totaling 1/6) develops a DLT during Cycle 1, the study will proceed to the expansion cohorts (Arm B) (see Section 6.4).
  - If ≥ 1 of these 3 additional patients (totaling ≥ 2/6) develop a DLT during Cycle 1, an additional 3 patients will be enrolled to receive the priming dose followed by Hu5F9-G4 (magrolimab) de-escalated to Dose Level -1 (20 mg/kg) during Cycle 1 (Table 4). The safety of Dose Level -1 will be similarly evaluated in 3-6 patients.
  - If 2 of the initial 3 patients develop a DLT during Cycle 1, an additional 3 patients will be enrolled to receive the priming dose followed by Hu5F9-G4 (magrolimab) de-escalated to Dose Level -1 (20 mg/kg) during Cycle 1. The safety of Dose Level -1 will be similarly evaluated in 3-6 patients.

Table 4: Doses for Hu5F9-G4 (magrolimab) and Dinutuximab during Dose Finding Cohort (Cycle 1)

Dose Level	Dose of (magrolimab)	Hu5F9-G4	Dose of Dinutuximab

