Level -1	20 mg/kg IV		17.5 mg/m  IV
Level 1	30 mg/kg IV		17.5 mg/m  IV

The dose level of Hu5F9-G4 (magrolimab) that is deemed safe during both the 'Single agent Safety Lead-In' and Cycle 1 in the dose finding cohort (Arm A) will be used to evaluate safety in the Arm B schedule. The first three (3) patients enrolled to Arm B will be evaluated for DLT, and three weeks (21 days) must elapse after completion of Cycle 1 in the final patient to allow for safety assessment before treating additional patients in Arm B to confirm the recommended phase 2 dose (RP2D) (Arm B) (see Section 6.2.1.2). These three patients will be allocated and analyzed in their respective cohorts for efficacy analysis.

If protocol therapy is delayed (due to re-scheduling for administrative reasons or temporary suspension due to toxicity), disease evaluations and correlative exploratory biology studies will follow the originally scheduled calendar dates and should *not* be adjusted for the dose delay. The results of these evaluations and assays while on treatment should reflect the effect of the former dose(s), not the current/prospective clinical status at the time of drug administration. All clinical assessments and laboratory tests (and their respective windows) will adjust with the dose delay to reflect the patient's clinical

status at the time of drug administration.

The Study Calendars in Section 11 outline the timing of procedures and visits for Arm A and Arm B.

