### 6.2.1.2 Expansion Cohorts (Arm B) Regimen

Once the RP2D is determined from the dose finding cohort, 4 expansion cohorts will be enrolled on Arm B on this study as defined in **Section 6.4**. Expansion cohorts B1-B3 will receive a priming dose of Hu5F9-G4 (magrolimab) (1 mg/kg) on week 1, followed in week 2 with Hu5F9-G4 (magrolimab) administered at RP2D on Day 1 and dinutuximab 17.5 mg/m^2 on Days 2-5. Hu5F9-G4 (magrolimab) will be administered at RP2D on Day 1 of week 3 and 4. A maximum of 12 cycles (see Table 6) can be completed in the absence of DLT or disease progression.

Patients in Arm B Cohort B4 will be enrolled in two subgroups:

- 1. Those who are scheduled for resection of lung lesion(s) (preferred), or those who have recently undergone resection of lung lesion(s) will start the Hu5F9-G4 (magrolimab)/dinutuximab within four weeks of resection as outlined in Section 6.4 and Table 6, and
- 2. Those who are scheduled for resection of lung lesions in a stepwise fashion. Patients in this group will initiate treatment between resections as described in Section 6.4. Prior to resection all patients will receive the Hu5F9-G4 (magrolimab)/dinutuximab as outlined in Table 6. If restart of Hu5F9-G4 (magrolimab)/dinutuximab occurs within four (4) weeks of the last dose of Hu5F9-G4 (magrolimab), the patient will pick up the regimen as per the next scheduled regimen cycle for a maximum of 5 cycles postoperatively.
  - If the restart of the Hu5F9-G4 (magrolimab)/dinutuximab is delayed beyond four weeks of the last dose of Hu5F9-G4 (magrolimab), the post-surgical regimen will be conducted as per Table 7 and will require a re-priming dose of Hu59-G4 (magrolimab).

Every attempt will be made to enroll to the "step-wise resection" subgroup prior to the first resection in order to obtain tissue from the resection for research correlatives. If subjects are enrolled after the initial resection, a request will be made

\*\* Cycles may be repeated as long as the patient does not have unacceptable toxicity (see Section 6.3 or Section Error! Reference source not found.) or disease progression to a maximum of 12 cycles

^ Hydroxyzine (0.5-1 mg/kg, Max dose 50 mg) PO may substitute for diphenhydramine

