Doses of Hu5F9-G4 (magrolimab) and dinutuximab in the expansion cohorts may be interrupted, delayed or discontinued depending on how well the participant tolerates the treatment. Dosing visits are not skipped, only delayed. Both Hu5F9-G4 (magrolimab) and dinutuximab must be delayed at the same time. Protocol therapy must be discontinued for dose delays greater than 14 days except for reasons outlined in **Section 6.6**. In such cases, the Protocol Principal Investigator must be consulted prior to resuming treatment.

For the expansion cohorts, patients will continue to be monitored for occurrence of DLT during Cycle 1. If 2 of the first 5 patients or if  $\geq$ 2 of 6 patients experience DLT, the Principal Investigator will discuss with all study investigators and with CTEP whether further addition of patients is needed to re-assess the RP2D.

Monitoring of all safety and toxicity data is done by the Principal Investigator and the Corresponding Organization on a real-time basis as data are entered into Medidata Rave using the Web Reporting Module. All participating sites are expected to notify the Principal Investigator when a DLT has occurred.

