# 9.2 Study Design/Endpoints

# **9.2.1** Dose Finding Cohort (Arm A) Primary Endpoint

The primary objective is to determine the safety and tolerability of Hu5F9-G4 (magrolimab) in combination with dinutuximab in children and young adults with relapsed/refractory (R/R) neuroblastoma (NBL) and osteosarcoma, and to determine the recommended phase 2 dose (RP2D) of Hu5F9-G4 (magrolimab) given in combination with dinutuximab. All patients who receive any amount of the study drug will be evaluable for toxicity. There will be two timepoints at which dose limiting toxicities (DLTs) will be measured to establish the maximum tolerated dose (MTD): during the 'single agent Safety Lead-In' in which patients with osteosarcoma or NBL will receive Hu5F9-G4 (magrolimab) during the first 3 weeks, and during Cycle 1 (21 days) of the combination of Hu5F9-G4 (magrolimab) and dinutuximab (Figure 2) as described in Section 6.3. If patients in the 'single agent Safety Lead-in' cohort or during Cycle 1 combination of Hu5F9-G4 (magrolimab) and dinutuximab discontinue participation prior to the safety evaluation for reasons other than the occurrence of a DLT (e.g., withdrawal of consent, rapid tumor progression, death due to rapid tumor progression, AE that does not meet DLT criteria), they will not be evaluable for MTD and will be replaced in the appropriate dose-finding group ('single agent Safety Lead-In' or Cycle 1 of Arm A).

If a patient is replaced to determine safety in Cycle 1 of Arm A, and the dose of Hu5F9-G4 (magrolimab) has NOT been deemed safe, i.e., 3 patients have not completed the Safety Lead-in without DLT, the replaced patient will undergo priming dose of Hu5F9-G4 (magrolimab), undergo the Safety Lead-in and then proceed to Cycle 1. This patient will be evaluable for DLT in the Safety Lead-in group.

If 3 patients have received Hu5F9-G4 (magrolimab) during the Safety Lead-in and the dose of Hu5F9-G4 (magrolimab) has been deemed safe, a patient being replaced in Cycle 1 of Arm A, will undergo a priming dose of Hu5F9-G4 (magrolimab) and proceed directly to Cycle 1 (combination of Hu5F9-G4 (magrolimab) and dinutuximab) for determination of MTD in the combination cohort.

Establishment of safety of the combination of Hu5F9-G4 (magrolimab) and dinutuximab will be completed in the first 3 patients enrolled in Arm B as described in section 6.1.1.2.

The safety and tolerability of Hu5F9-G4 (magrolimab) plus dinutuximab will be assessed by:

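### The three-patient Arm B check has no DLT count that confirms or fails the RP2D, and the Section 6.4 trigger requires a discussion but no enrolment pause or dose decision

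*Combined protocol and SAP*

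**What the plan says.** **Arm A** has written consequences for each DLT count. For Cycle 1, Section 6.1.1.2 lets 0/3 proceed to Arm B. For one event it says "If 1 of the initial 3 patients develops a DLT during Cycle 1, then an additional 3 patients will be enrolled". For 2 of the first 3, or 2 or more of 6, "an additional 3 patients will be enrolled to receive the priming dose followed by Hu5F9-G4 (magrolimab) de-escalated to Dose Level -1". At 20 mg/kg in the lead-in, 2 or more DLTs mean that "enrollment will pause pending discussions with the sponsor, IRB and FDA" (Section 6.1.1.1). The schema note is stricter: "If ≥ 2 DLTs at DL-1, then STOP study".

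**Arm B** takes the dose cleared in Arm A onto a schedule without the single-agent lead-in. Under Section 6.2.1.2 the priming dose is "followed in week 2 with Hu5F9-G4 (magrolimab) administered at RP2D on Day 1 and dinutuximab" on Days 2-5. Section 6.1.1.2 adds a check: "The first three (3) patients enrolled to Arm B will be evaluated for DLT", and other Arm B patients wait until 21 days after the third patient completes Cycle 1. The stated purpose is to confirm the RP2D. Section 9.2.1 says "Establishment of safety of the combination of Hu5F9-G4 (magrolimab) and dinutuximab will be completed in the first 3 patients enrolled in Arm B" and points back to 6.1.1.2 for the method.

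Section 6.4 continues DLT monitoring in Cycle 1 of the expansion cohorts. At 2 of the first 5 patients, or 2 or more of 6, "the Principal Investigator will discuss with all study investigators and with CTEP whether further addition of patients is needed to re-assess the RP2D".

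**The concern.** A confirmatory check needs a result that would fail to confirm. Section 6.1.1.2 names none: the hold lasts 21 days whether 0, 1, 2 or 3 of the three patients have a DLT. Section 6.4 does supply a count, but it leads to a question about adding patients, not to a decision on the dose.

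The binding rules do not carry over. The schema's reduction to 20 mg/kg is tied to weeks 3 and 6, which are Arm A assessment points; Arm B Cycle 1 occupies weeks 2-4. The de-escalation footnote belongs to Table 5, the Arm A regimen. The Arm B regimens in Tables 6 and 7 say only that the dose was set in the dose-finding cohort.

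The check has real work to do. In Arm B the first full magrolimab dose falls the day before the first dinutuximab dose. Section 7.2.1 says infusion reactions occur mainly with the first two magrolimab doses, and Section 10.1.1.2 raises a theoretical risk of worse pain or nerve toxicity with the combination. Safety and the RP2D are primary objectives. With the plan followed exactly, patients could continue to start treatment at a dose that Arm A's own limits would reject.

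**Working it through.** The documents give no operating characteristics for the Arm B check or the 6.4 trigger, so there is no stated figure to reproduce.

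**Inputs**
- Check size 3, followed by one 21-day hold (6.1.1.2).
- Trigger: 2 of the first 5, or 2 or more of 6 (6.4). The first condition is contained in the second, so the trigger amounts to 2 or more of 6.
- Assumption: DLTs are pooled across B1-B4 and include the first three patients. Section 6.4 does not say so, but this is the natural reading.
- Assumption: true DLT rate p = 20%, 33% (taken as 1/3) or 50%, independent between patients. The documents state no target rate. Write q = 1 - p.

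**Step 1. How often the trigger is met.** P(2 or more of 6) = 1 - q^6 - 6pq^5.

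**Step 2. How often it is met within the existing hold.** P(2 or more of 3) = 3p²q + p³.

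**Step 3. How often it is met with no hold in force.** There are two routes: 1/3 then at least 1 of the next 3, which is 3pq²(1 - q³); and 0/3 then at least 2 of the next 3, which is q³(3p²q + p³).

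**Step 4. Comparison with Arm A's limits.** P(3+3 rejects) = 1 - (q³ + 3pq² × q³).

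| | p = 20% | p = 33% | p = 50% |
|---|---|---|---|
| Trigger met | 0.345 | 0.649 | 0.891 |
| of which within the hold (2 or 3 of first 3) | 0.104 | 0.259 | 0.500 |
| of which after 1/3 | 0.187 | 0.313 | 0.328 |
| of which after 0/3 | 0.053 | 0.077 | 0.062 |
| **Trigger met, no hold in force** | **0.241** | **0.390** | **0.391** |
| 3+3 would reject | 0.291 | 0.572 | 0.828 |

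The no-hold row is also the difference of the first two: 0.345 - 0.104, 0.649 - 0.259 and 0.891 - 0.500.

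The trigger exceeds 3+3 rejection by exactly the 0/3 route (at 20%, 0.345 - 0.291 gives 0.053 before rounding). It therefore contains every outcome that Arm A's rule would reject. Detection is adequate; the missing part is what must happen next.

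**The case against.** **The worst outcomes are already held.** If 2 or 3 of the first 3 have a DLT, the trigger is met while no further Arm B patient may start. This stands, and it removes 0.10, 0.26 and 0.50 from the trigger probabilities. The protection is partial, because the hold lapses on a date and not on a decision.

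**Oversight exists.** Sites must notify the Principal Investigator of each DLT and data are monitored in real time (6.4). Each enrolment needs a slot reservation and notice to the Study Chair or Vice Chair (4.3.3). DLT evaluations go to a weekly call (13.1.2). Any of these could stop accrual in practice, but none is tied to a DLT count.

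**Discussion is a defensible choice.** The dose has already passed Arm A. Two of six in Arm B after 0/3 or 1/6 in Arm A Cycle 1 pools to 2/9 or 3/12, that is 22% to 25%, where automatic de-escalation is debatable. With an unchanged 50% rate, a dose would pass Arm A's Cycle 1 rule only 17% of the time (1 - 0.828), so the last column matters mainly if the Arm B schedule itself adds toxicity. This argues against a forced dose cut. It does not argue against pausing while the decision is made.

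**The schedule may not be wholly untested.** Some Arm A replacement patients go from priming straight to Cycle 1 (9.2.1). If Arm A de-escalates during Cycle 1, the 20 mg/kg patients appear to do so too. The gap therefore matters most at 30 mg/kg.

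**Conclusion.** The point holds. The check meant to confirm the RP2D has no failing result. The one Arm B threshold requires a consultation, but no enrolment pause and no dose decision before more patients are treated. The exposed outcome is a trigger reached after 0/3 or 1/3, with probability about 0.24, 0.39 and 0.39 at true DLT rates of 20%, 33% and 50%. These figures rest on the assumed rates, independence and a pooled reading of 6.4.

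Three stronger readings are tempting and are not supported:
- **That excess toxicity would go undetected.** The 6.4 trigger covers every 3+3 rejection, and its discussion is mandatory.
- **That Arm B has no pause, so that 0.34, 0.65 and 0.89 is the chance of unpaused enrolment.** The 21-day hold covers 2 or 3 DLTs in the first 3 until it expires.
- **That parity with Arm A demands a second hold, or that de-escalation must be automatic.** Arm A has a single 21-day hold, after its final patient. Automatic de-escalation in Arm B is a trade-off.

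**What to change.** **Section 6.1.1.2:** state that 0/3 confirms the RP2D on the Arm B schedule, subject to the 6.4 trigger. After 1/3, the next three Arm B patients complete the DLT evaluation, and 1/6 confirms. Two or more DLTs among the first 3 to 6 patients mean the dose is not confirmed.

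**Section 6.4:** state that DLTs are pooled across B1-B4, including the first three patients. Once the trigger is met, no new Arm B patient starts treatment until the Principal Investigator and CTEP document a decision: continue, reduce to 20 mg/kg, change the schedule (for example, restore the lead-in), or stop. If the dose is already 20 mg/kg, say whether the schema's stop rule applies, or the 6.1.1.1 pause pending sponsor, IRB and FDA discussion.

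**Optional:** de-escalation as the default, and a second 21-day hold after patient 6. That hold would end 7 + 21 + 21 = 49 days after patient 6's first dose. At the stated 2-3 patients a month, about 3 to 5 starts would wait (49/30.4 × 2 = 3.2; × 3 = 4.8).

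**Cost:** protocol wording and a possible accrual pause. At a true DLT rate of 20% the pause would be triggered with probability about 0.34, even though Arm A had cleared the dose; allowing a documented decision to continue keeps that cost to time. If the dose is cut from 30 mg/kg, the 3 to 6 patients treated there would need replacing. On the plan's own budget of six places per dose level, the six unused Dose Level -1 places cover this (6 + 6 + 70 = 82), so the maximum need not rise.

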# 6.2 Regimen Description and Supportive Care Guidelines

- **6.2.1** Hu5F9-G4 (Magrolimab) and Dinutuximab (Unituxin®) Agent Administration
- 6.2.1.1 Dose Finding Cohort (Arm A) Regimen

Table 5: Regimen Description for Dose Finding Cohort (Arm A)

Agent	Premedications; Precautions	Dose	Route	Schedule	Cycle Length
Hu5F9-G4 (magrolimab)	Administer according to guidelines in Section 6.2.1.3. Acetaminophen oral (PO) and diphenhydramine (IV) or a comparable regimen up to 15 minutes before the first two doses of Hu5F9-G4 (magrolimab), and in case of re-priming of the patient after > 4 weeks interruption in treatment. Monitor for infusion reactions during and	mg) of acetaminophen; 0.5 - 1 mg/ kg (max 50 mg) of diphenhydramine^  Priming: Hu5F9-G4 (magrolimab) - 1 mg/kg  "Single Agent Safety Lead-In": Hu5F9-G4 (magrolimab) 30 mg/kg*  Cycles 1 and subsequent cycles: Hu5F9-G4 (magrolimab) 30	PO; Diphenhydramin e IV  Priming: Infuse IV (peripheral or central line) over 3 hours (± 30 min)  Subsequent infusions: Infuse IV over 2 hours	-	21 days (3 weeks)
Dinutuximab	Administration requires premedication	10 mg/kg (max 650 mg) of		Cycles 1 (Week 1): Days 2-5;	

(acetaminophen -	- 1 mg/ kg (max 50	e^ IV (no need to	Cycle 2 (Week
oral,	0 0 1	be repeated if	` `
diphenhydramine -	O ,	dinutuximab	-,- = -,-
IV, and analgesia)			Subsequent
and hydration prior to		follows previous	
initiation according to		drug infusion)	
Section 6.2.1.4	Dinutuximab - 17.5		week of each
	$mg/m^2$	Analgesia as	subsequent
		described below	cycle
		in Section	
		6.2.1.4 .	
		Dinutuximab in	
		100 mL bag of	
Administer 0.9%		0.9% Sodium	
Sodium Chloride		Chloride	
Injection USP 10		Injection USP	
mL/kg as an IV over 1		(mix by gentle	
hour prior to initiating		inversion - DO	
drug infusion		NOT shake)	

\* Dose will be de-escalated to 20 mg/kg if 2 or more patients develop DLT during the "Single Agent Safety Lead-In" or Cycle 1.

